Next visit will be performed after at least 24 sachets have been taken (i.e. 4 or 5 days after the first visit (i.e. Day 5 or Day 6)).

Under no circumstances will subjects be enrolled more than once. Each investigator will also maintain a record of all subjects enrolled into the study (i.e. who signed the informed consent form). Records up to the time of premature termination should be completed. In the event that the subject was not receiving IMP, the primary reason will be recorded.

5.2.2 *Visit 2 (follow-up or End of study, Day 5 or Day 6)*

The following procedures will be performed:

- Adverse events will be reported by subject since the last visit and will be collected.
- The Investigator will check in the DEB if clinical data were appropriately recorded and if the study drug was appropriately used.
- Any change in the concomitant medication and/or surgical procedures since Visit 1 will be checked and recorded in the eCRF.
- A physical examination and body weight measurement will be performed.
- Vital signs (blood pressure, heart rate in sitting position, respiratory rate, body temperature and body weight) will be checked.
- Faecal microbiological results will be recorded
- Visit Status will be recorded

In case of recovery, the study treatment will be stopped. A last visit (Visit 3) will be planned at Day 9 or 10 for subjects who did not recover by Visit 2

5.2.3 *Visit 3 (End of study if patient is not recovered at Visit 2, Day 9 or Day 10)*

- Adverse events will be reported by subjects since the last visit and will be collected until 7 days after the last treatment intake.
- Any change in the concomitant medication and/or surgical procedures since Visit 2 will be checked and recorded in the DEB.
- A physical examination and body weight measurement will be performed.
- Vital signs (blood pressure, heart rate in sitting position, respiratory rate body temperature and body weight) will be checked.
- The Investigator will check in the DEB if clinical data were appropriately recorded and if the study drug was appropriately used. A copy of the DEB will be kept in the subject's file and the original will be sent to the Sponsor (Data Management).
- Visit Status will be recorded

Treatments units with used and unused sachets will be kept by the investigator.

5.2.4 *Early Withdrawal Visit*

- Adverse events will be reported by subjects since the last visit and will be collected until 7 days after the last treatment intake.

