7.3 Microbiological Tests

A fresh stool will be collected as soon as possible after inclusion for microbiological laboratory testing (for virology, bacteriology and parasitology testing) in order to determine the microbiological status of this acute diarrhoea episode , i.e. the absence/presence of the following faecal pathogens:

Virology testing

- rotavirus,
- adenovirus,
- norovirus,

Bacteriology and parasitology testing

- enteropathogenic and Enterotoxigenic Escherichia Coli (E. coli),
- staphylococcus aureus,
- shigella,
- salmonella,
- campylobacter,
- yersinia enterocolitica,
- amoebiasis (entamoeba histolytica),
- giardia / lamblia.

Details of the methodology and technical specifications will be provided in the laboratory manual located in the Investigator Site File and in the TMF.

Laboratory test results provided by the lab will be recorded in the laboratory results section of the eCRF by the investigator at Visit 2.

7.4 **Methods and Timing of Assessing, Recording, and Analysing Efficacy Data**

The subject will be asked to complete, each day from Day 1 (day of Visit 1) to the end of the treatment visit (Visit 2 (Day 5 or Day 6) or Visit 3 (Day 8 or Day 9)), the DEB with the following information:

- Stools:
 - date and time to onset,
 - consistency rated as either watery, loose, formed or hard (according to the Bristol scale; see [Appendix 3](#)),
- Presence or not of an episode for each 12-hour period:
 - nausea,
 - vomiting,
 - abdominal pain
 - anal irritation.
- abdominal pain intensity (rated with a 5-point ordinal scale: 0 = absent, 1= mild, 2 =moderate, 3 = severe, 4= very severe)
- Study drug consumption (number of sachets per day)

Methods for assessing efficacy data are described above in Section 7.1 and Section 7.2. Timing of efficacy assessments are discussed in Section 5. Procedures for recording efficacy data are discussed in Section 14.1, and methods of analysis are discussed in Section 10.4.5.

8 **ASSESSMENT OF SAFETY**

8.1 **Adverse Events**

Adverse events will be monitored from the time that the subject gives informed consent and throughout the study until 7 days after the end of study treatment (see Section 3.5 for a definition of the study duration) and will be elicited by direct, non-leading questioning or by spontaneous reports. Further details for AE reporting can be found in Section 8.1.2.

8.1.1 ***Definition of an Adverse Event***

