3.1.4 Multiplicity

No adjustments for multiple testing are planned. Only primary analysis of the primary endpoint (ITT population) will be considered confirmatory.

3.1.5 *Significance testing and estimation*

All statistical tests will be performed two-sided with a type I error rate set at (5%). For any efficacy endpoints, the 95% confidence interval (CI) of the difference between treatment groups will be calculated when appropriate.

3.2 **Analysis methods**

3.2.1 *Efficacy*

3.2.1.1 *Primary efficacy analysis*

(a) Main analysis

The primary analysis of efficacy data will be performed on the ITT population.

The primary endpoint (time from the first study treatment intake (T0)) to recovery defined as 1st formed stool followed by a nonwatery stool (in hours), will be analysed using a time to event methodology.

Any stool recorded before dosing should not be taken into account in the analysis.

The time to recovery will be given in hours and will be analyzed using the Kaplan Meier (KM) survival analysis method (see SAS syntax hereafter). The median recovery time, first and third quartiles with their 95% CIs will be estimated for each treatment group using KM product-limit estimation. In addition, KM cumulative estimators will be computed for recovery rates at 12, 24, 36, 48, 60, 72, 84, 96 hours and estimates for every 12 hours thereafter as applicable.

Results will be also presented graphically in Kaplan-Meier plots.

The primary analysis will test the equality of time to recovery between the two treatment groups, applying the two-sided Gehan-Wilcoxon test ($\alpha = 5\%$) based on the ITT set.

The following Null-hypothesis is tested:

$$H_0: \lambda_A(t) = \lambda_B(t) \text{ versus } H_1: \lambda_A(t) \neq \lambda_B(t),$$

where $\lambda(t)$ represents the hazard at time t, A=diosmectite and B=placebo.

CCI

Subjects prematurely withdrawn without recovery or ending the study without recovery will be censored (not responder) at their last date/time of stools as recorded in the DEB.

Special cases of censoring: subjects who have not filled in the DEB (i.e. no post baseline evaluation regarding "stool number" and "consistency" according to Bristol scale) will be censored at the date and time of their first study drug intake (or the randomisation date time if not administered).

A frequency table of reasons of censoring will be displayed by treatment group.

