3.2.1.2 Secondary efficacy analysis

The analysis regarding secondary efficacy endpoints will be performed on the ITT population. Supportive analysis using PP population will be carried out if more than 10% of subjects are excluded from ITT set.

Rules for handling incomplete dates and times recorded on the DEB are described in section 3.2.3.2.

(a) Abdominal pain intensity per 12-hour period

Intensity of abdominal pain per 12-hour period will be summarized by treatment group (an absence of pain will be considered as value zero).

Considering the ordinal nature of the outcome, difference between diosmectite and placebo will be studied by fitting a cumulative logit model assuming an ordered multinomial response distribution. The model will include treatment group as fixed effects and a random intercept effect. Contrasts between diosmectite and placebo will be given in term of odds ratios (modelling the probabilities to obtain higher scores of pain intensity). The model will be performed for each time point (12-hour period) separately (see SAS Syntax below).

CCI
[Redacted]

(b) Time from diarrhoea onset to recovery

This endpoint is a time to event endpoint which will be analysed using the same methodology as for the primary efficacy endpoint. The date and time of diarrhoea onset will be the start date and time of diarrhoea onset as recorded from the "History

of current acute diarrhoea episode” eCRF section. Subjects will be censored using the same rules as defined for the primary endpoint.

(c) Time from diarrhoea onset to the first formed stool.

This endpoint is a time to event endpoint which will be analysed using the same methodology as for the primary efficacy endpoint.

(d) Time from the 1st study treatment intake to the last watery stool.

This endpoint is a time to event endpoint which will be analysed using the same methodology as for the primary efficacy endpoint.

(e) Number of stools, per 12-hour period.

Number of stools per 12-hour period (0-12h, 12-24h, 24-36h...) will be computed by summing the number of stools as recorded in the DEB by the subject using the time (24-hour clock) of visit to restrooms. The number of stools per 12-hour period will then summarized by treatment group. From first to last intake, if no stool is reported in the diary at a specific time interval, the number of stools at the considered 12-hour period will be considered as zero.

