Any stool with a missing evaluation consistency should be counted in the total number of stools per 12-hour period (if time of stool is not missing).

Any stool with a missing time, with a consistency evaluation and which is embedded within the same time interval will be counted in the number of stools for the considered time interval. The number of stools per 12-hour period during the post baseline period will be analysed with an analysis of covariance (ANCOVA) method with repeated measurements. The model will include number of stools 24 hours before randomisation (baseline) as covariate, treatment, time point (12-hour period until visit 3), the treatment by time point interaction as fixed effects and subject as random effect. The residual variance-covariance pattern will be fitted using an unstructured matrix (see SAS Syntax below). Adjusted means, 95% CIs and corresponding p-values of differences between diosmectite and placebo, derived from the model, will be displayed globally and for each time point.

CCI

[REDACTED]

If the model fails to converge, only time intervals with a sufficient number of patients could be included in the model.

In the event of gross violations from the normality assumptions (identified using the shape of the distribution and QQ plots of change from baseline overall and by visit) or from the covariance model assumptions or in case of convergence criterion fails to be reached, a non-parametric analysis will be used instead (Mann-Wilcoxon-Mann-Whitney test (see SAS syntax below)) at each time point separately.

CCI
[REDACTED]
[REDACTED]
[REDACTED]
[REDACTED]
[REDACTED]
[REDACTED]

In addition the cumulative number of stools per 12-hour period will be presented graphically using barcharts of means (\pm SEM) on observed values at each time point by treatment group.

(f) Number of watery stools, per 12-hour period.

The same analysis as described above will be performed for number of watery stools (corresponding to type 6 or 7). The model will include, as fixed effects, number of watery stools 24 hours before randomisation, treatment, time point (12-hour interval) and the treatment by time point interaction effect.

(g) Percentage of subjects with associated symptoms such as nausea, vomiting, abdominal pain and anal irritation, per 12-hour period.

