Note: In the event of multiple occurrence of a same AE (same Preferred Term) by the same subject, the maximum intensity (severe > missing > moderate > mild) and the most serious causality (related > not related) will be chosen.

SAP Final Version: 15 July 2019

27/50

Note: In case of missing data for relationship/intensity, the AE (PT) will be presented with the most severe category (related and/or severe) when crossing intensity and relationship.

3.2.2.2 *Laboratory data*

Not applicable.

3.2.2.3 *Vital signs*

Vital signs will be listed at each assessment by treatment group and subject. Any unscheduled vital signs will be flagged [U] in the listing.

Baseline values (values at first visit) will be defined as the last vital signs measurement collected prior to the first dose of study drug.

Summary statistics by treatment group will be presented (blood pressure, heart rate in sitting position, body temperature and body weight) at each scheduled assessment for actual values and changes from baseline.

3.2.2.4 *ECG*

Not applicable.

3.2.2.5 *Other assessments (as applicable)*

Any new or worsening clinically significant abnormal physical examination results should be recorded on the Adverse Event eCRF page and will be part of the AE analysis.

3.2.3 *Missing data and outliers*

3.2.3.1 *Missing data*

If there is a significant number of missing values for a subject (or if there is confirmed data appearing spurious), a decision will be made following consultation with the sponsor regarding the handling of these data in summaries, prior to breaking the blind.

Any repeat or additional assessments performed will be included in the individual subject data listings.

3.2.3.2 *Missing or incomplete dates*

Missing date and/or time related to stools in patients diaries for time-to-event analyses (time to recovery, time to first formed stool, time to last watery stool, time to recovery without confirmation):

Rules of imputation for events: in case of time information is missing but information on date and on stool consistency are available, the time will be imputed:

- to 23:59 if there is no other subsequent stools the same day,
- to time of the next stool the same day minus 1 minute otherwise.

Rules of imputation for censoring: in case of time information is missing but information on date and on stool consistency are available, the time will be imputed:

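### Per-12-hour secondary tests run past Visit 2, when only unrecovered subjects are still followed, and stool-free periods stop counting as zero at the last sachet

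*SAP*

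**What the plan says.** - **Periods and tests.** SAP 3.2.1.2(e) fits a repeated-measures model over "time point (12-hour period until visit 3". Adjusted differences, confidence intervals and p-values are reported globally and for each period. Endpoint (f), watery stools, uses the same analysis.
- **Other per-period endpoints.** For pain (a), "The model will be performed for each time point (12-hour period) separately". For symptoms (g), the effect is assessed at each 12-hour period. Neither states a last period.
- **Follow-up.** SAP 1.2 and 1.2.2 give a Visit 3 only to subjects not recovered at Visit 2; the others end at 5 to 6 days. Protocol 7.4 has the diary kept "each day from Day 1 (day of Visit 1) to the end of the treatment visit", which is Visit 2 or Visit 3. On the timing of Visit 2, Protocol 5.2.1 says: "Next visit will be performed after at least 24 sachets have been taken (i.e. 4 or 5 days after the first visit".
- **Zero rule in (e).** "From first to last intake, if no stool is reported in the diary at a specific time interval", the count is taken as zero. Treatment may stop on recovery once 24 sachets have been taken (Protocol 3.1 and 6.1; SAP 1.2). Protocol 10.4.5 does not replace missing secondary data.
- **Possible safeguards.** In (e): "If the model fails to converge, only time intervals with a sufficient number of patients could be included in the model". In SAP 3.2.3.1, for a subject with many missing values: "a decision will be made following consultation with the sponsor regarding the handling of these data in summaries, prior to breaking the blind".
- **Status.** SAP 3.1.4: "Only primary analysis of the primary endpoint (ITT population) will be considered confirmatory".

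**The concern.** There are two separate problems.

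**Selection after Visit 2.** Whether a subject contributes to a late period depends on not having recovered by Visit 2, which is the primary outcome. If treatment speeds recovery, the two late subsets differ in size and in kind, and their comparison is no longer protected by randomisation. The repeated-measures model in (e) and (f) conditions on earlier counts, so it is partly protected. The separate pain models, the charts of observed values and the period-by-period Mann-Whitney fallback have no protection.

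**Zero-filling tied to the last sachet.** A recovered subject may stop treatment after 24 sachets and still keep the diary until Visit 2. In that gap a stool-free period is not set to zero, while a period containing a stool still counts. Read with the protocol's no-replacement rule, whether a period enters the analysis then depends on its own value.

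At stake is the secondary objective of showing superiority on other efficacy criteria. The per-period and global p-values will be read as evidence on it.

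**Working it through.** **1. The plan's own figure.** The documents give no number for the 12-hour endpoints, so the only figure to reproduce is the sample size (SAP 1.3.4). With exponential recovery and medians of 55 and 70 h, the hazard ratio is 55/70 = 0.786. Log-rank events are 4 × (1.960 + 0.842)² / (ln 0.786)² ≈ 540. Dividing by 0.75, the efficiency of Gehan-Wilcoxon relative to log-rank under proportional hazards without censoring, gives 720, or 360 per arm. A direct calculation gives 362. The plan says 363, and 363/0.85 = 427. An exponential shape is therefore consistent with the plan's sizing, though not stated in it.

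**2. Share unrecovered.** S(t) = 2^(−t/median).

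| Time | Active | Placebo |
|---|---|---|
| 96 h | 29.8% | 38.7% |
| 108 h | 25.6% | 34.3% |
| 120 h | 22.0% | 30.5% |

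Assumed clock times: first intake uniform 08:00 to 19:00; Visit 2 uniform 08:00 to 17:00, not before the 24th sachet, evenly on Day 5 or 6. Visit 2 then falls between 86 and 129 h. Averaged over these times, 26.2% and 34.8% are unrecovered at Visit 2, about 112 and 149 of 427. The earliest case is a first intake at 18:00: 4 + 18 + 2 = 24 sachets by the morning of Day 5, and an 08:00 visit is at 104 − 18 = 86 h.

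**3. Late means.** Assumed rates, not in the documents: 1.75 stools per 12 h before recovery and 0.5 after. With share u unrecovered, the mean is 0.5 + 1.25u. At 132 h every Visit 2 has passed, and among those still followed u = S(132)/S(Visit 2).

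| At 132 h | Active | Placebo | Difference |
|---|---|---|---|
| All randomised | u = 0.190, mean 0.74 | u = 0.271, mean 0.84 | −0.10 |
| Still followed | u = 0.190/0.262 = 0.72, mean 1.40 | u = 0.271/0.348 = 0.78, mean 1.47 | −0.07 |

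Allowing recovery speed to vary between subjects, with slow recoverers more symptomatic, widens the placebo figures from 132 h to about 1.4–2.0 observed against 0.8–1.1 in all randomised subjects. This holds whether or not part-periods are kept.

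**4. Zero rule alone, 96–108 h.** Let f be the share of recovered subjects already off treatment. The mean over counted periods, using S(96), is

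[1.75 S + 0.5 (1 − S)] / [S + (1 − S)(1 − f) + (1 − S) f (1 − e^(−0.5))].

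| f | Active | Placebo |
|---|---|---|
| 0 (correct) | 0.87 | 0.98 |
| 0.5 | 1.11 | 1.21 |
| 1 | 1.52 | 1.57 |

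**5. Direction of the modelled contrast.** A separate simulation used 427 per arm, 16 periods, unstructured covariance, the SAP's zero rule, Visit 2 at 108 h, and assumed rates of 2.0 and 0.6. Global contrast, active minus placebo:

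| Scenario | Full follow-up | As planned | 0–96 h: full follow-up / as planned |
|---|---|---|---|
| Equal rate while unrecovered | −0.103 | about −0.07 | −0.095 / −0.096 |
| Severity drives recovery and stool rate | −0.090 | about −0.03 | −0.069 / −0.067 |
| Drug also lowers stool rate by 20% while unrecovered | −0.250 | about −0.34 | −0.320 / −0.330 |

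In the second scenario the raw late contrast changed sign (−0.112 to +0.049). These rows show that the direction is open; they are not bounds. Restricting the contrast to periods before Visit 2 removed the distortion in all three.

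**The case against.** **Safeguards exist.** The non-convergence rule is optional and applies only if the model fails. With over 100 subjects per arm still followed at Visit 2, it may never apply. The blinded missing-data decision concerns individual subjects with many missing values, and the protocol's proviso that models are fitted only where the data allow sets no last period. They leave room for a restriction but do not make one.

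**A reader might infer that late effects are always diluted, or that means are inflated throughout the Visit 2 window.** The documents do not support this. The SAP does not say how a period cut short by the final visit is handled. With part-periods kept, empty ones set to zero and no severity mix, the placebo mean at 96–108 h is nearly right (1.00 against 0.96). At 120–132 h it is 1.12 against 0.86, and the observed difference is enlarged (−0.16 against −0.10). Only from 132 h does inflation of the observed means hold under either convention.

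**A reader might infer that the SAP drops stool-free periods after the last sachet.** It is silent on them. Dropping is a reading based on the protocol's no-replacement rule, and the model syntax is blacked out. Protocol 5.2.2 also describes treatment stopping at Visit 2 on recovery, in which case the gap would be short.

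**Extending the point to (a) and (g) is conditional.** The Visit 3 end point is written only for (e) and carries to (f).

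**Precision.** With 112 and 149 subjects and Poisson means of 1.5 to 2.0, the standard error of one late contrast is √(1.5/112 + 1.5/149) = 0.15 to √(2/112 + 2/149) = 0.18. A shift in one period may be lost in noise. That stands, but a late p-value still does not test the randomised comparison.

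**Conclusion.** The point holds. As written, (e) and (f) test treatment in periods where only subjects unrecovered at Visit 2 are followed, about 26% and 35% of the arms. The same selection reaches (a) and (g) if they run past Visit 2. Separately, the zero rule stops at a time that recovery itself can determine.

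The 26% and 35% rest on the plan's medians plus exponential recovery and an even Day 5/6 split; withdrawals are ignored. The late placebo means of 1.4–2.0 against 0.8–1.1 also rest on assumed stool rates. The effect on treatment contrasts depends on recovery shape, severity mix, visit timing and part-period handling, so neither a direction nor a range should be quoted.

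The primary analysis, the only confirmatory one, is untouched. This should be corrected because the secondary p-values would otherwise be hard to interpret; it does not threaten the trial's main conclusion.

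**What to change.** 1. In (e) and (f), set stool-free periods to zero through the last completed diary day instead of the last sachet, and state how a period cut short by the final visit is treated.
2. For (a), (e), (f) and (g), limit between-group tests and the global contrast to periods that end before recovered subjects' follow-up ends. Fix the last period at the blind data review from actual Visit 2 times, arms pooled, so that it ends before Visit 2 for essentially all subjects. Under the assumed clock times that is 84 h. If a later cut is chosen for (e) and (f), which the model partly protects, state the share already past Visit 2; at 96 h it would be about 30% under the same assumptions. Show later periods descriptively, with the number still followed per arm.
3. Record this in SAP section 5, which now lists no changes, because Protocol 10.4.5 asks for the effect at each 12-hour period for the binary endpoints and defines the others per period.

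The cost is SAP text and one section 5 entry before unblinding, with no new data. The downside is that late periods carry no p-values.

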The proportion of subjects with at least one associated symptom will be displayed per treatment group and per 12-hour period, using data retrieved from the DEB for post baseline values and using data retrieved from the eCRF for baseline value (Presence of associated symptoms during the last 24 hours from the “History of current acute diarrhoea episode” page). Same results will be displayed for each symptom separately: nausea, vomiting, abdominal pain and anal irritation. To assess the treatment effect at each 12-hour period on associated symptoms overall and on each symptom separately, a non-linear mixed model will be used including treatment and status of subjects at baseline (With or without associated symptoms), time-point and treatment by time-point interaction as fixed effects and number of watery stools during 24h prior inclusion as covariate (see SAS Syntax below).

CCI
[REDACTED]
[REDACTED]
[REDACTED]
[REDACTED]
[REDACTED]
[REDACTED]
[REDACTED]
[REDACTED]
[REDACTED]

In addition the percentage of subjects (with at least associated symptom and for each symptom separately) per 12-hour period will be presented graphically using barcharts at each time point by treatment group.

3.2.2 *Safety*

All safety data will be included in the data listings and summary tables will be based on the safety population.

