- 12-hour period (for analysis of number of stools and number of watery stools): is defined as the number of hours between the date/time of stool recorded in the DEB and the date/time of first IMP intake and will be expressed in time intervals of 12 hours ([0-12h], [12-24h], [24-36h]....).

Other derived variables

The following derived data will be calculated and included in the listings:

- **Study day**

Study day based on the 1st treatment intake will be calculated as following:

If the date was on or after treatment intake then

$$\text{Study day} = \text{Date} - \text{date of study treatment intake} + 1$$

If the date was before treatment intake then

$$\text{Study day} = \text{Date} - \text{date of study treatment intake}.$$

- **Study exposure (days)**

Study exposure (days) will be calculated as follows:

$$\text{Exposure (days)} = (\text{Date of Last Study Visit} - \text{Date of Informed Consent} + 1).$$

- **Study Drug Exposure (days)**

$$\text{Drug exposure (days)} = (\text{last sachet intake date} - \text{first sachet intake date} + 1).$$

- **Compliance (%)**

Compliance of study medication will be calculated as follows:

$$\text{Compliance (\%)} = (\text{Total sachets taken} / \text{Expected total sachets}) \times 100.$$

(a) During the mandatory treatment period:

Expected total sachets = 24 therefore,

$$\text{Compliance} = (\text{Total sachets taken from Day1 to Day4 or Day5}) / 24.$$

The number of sachets taken by the patient during the mandatory period will be derived according to the time of day at which the subjects has taken the first of two sachets on day 1: in the morning if the first two sachets have been taken before 11:00 a.m. (<11:00 a.m.), the afternoon if taken between 11:00 a.m. and 6:00 p.m. ([11:00 a.m.; 6:00 p.m.]) and the evening if taken after 6:00 p.m. (>6:00 p.m). Patients with a missing time of first administration will be considered to have taken their first two sachets in the morning (i.e. before 11:00 a.m.).

(b) Until recovery for subjects with recovery:

Expected total sachets will be calculated using date and time of recovery according to diary:

Expected total sachets = (Date of confirmation of Recovery – Date of 1st sachet intake +1) * 6⁽¹⁾ ⁽²⁾.

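### The stool-count model's subject random effect duplicates its unstructured matrix, and the per-period pain model's random intercept, if at subject level, is barely identifiable and makes its odds ratios unstable

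*SAP*

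**What the plan says.** **Stool counts, SAP 3.2.1.2 (e).** The repeated-measures ANCOVA has baseline stool count, treatment, 12-hour period up to Visit 3, "the treatment by time point interaction as fixed effects and subject as random effect". The next sentence adds: "The residual variance-covariance pattern will be fitted using an unstructured matrix". There are two responses to non-convergence. The first is "If the model fails to converge, only time intervals with a sufficient number of patients could be included in the model". The second is that "in case of convergence criterion fails to be reached, a non-parametric analysis will be used instead", namely a Wilcoxon-Mann-Whitney test at each time point. Part (f) applies the same analysis to watery stools, but its own list of terms has no random effect. Protocol 10.4.5 specifies the fixed effects and the unstructured matrix and names no random subject effect.

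**Abdominal pain, SAP 3.2.1.2 (a).** A cumulative logit model is specified: "The model will include treatment group as fixed effects and a random intercept effect". Also: "The model will be performed for each time point (12-hour period) separately". Results are reported as odds ratios for higher pain scores. The grouping unit of the intercept is not stated and the code is redacted. SAP 1.3.2.1 gives one pain rating per subject per period. No baseline covariate is listed, although abdominal pain (yes/no) over the 24 hours before entry is collected at Visit 1 (Protocol 5.2.1; SAP 1.3.2.3) and model (g) adjusts for baseline symptom status.

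**The concern.** In (e), a subject random effect adds one constant to every element of the within-subject covariance matrix. An unstructured matrix already allows every element to take any admissible value, so the data cannot separate the two. The surplus parameter makes the information matrix singular. That can produce a convergence failure unrelated to the data, which the SAP would answer by dropping intervals and then abandoning the adjusted model.

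In (a), a random intercept normally represents correlation among repeated ratings. Each separate fit has only one rating per subject, so a subject-level intercept has no such correlation to describe. Its variance can be estimated only through small departures from proportional odds between the arms. Because a conditional odds ratio moves away from 1 as that variance grows, a nearly arbitrary variance estimate makes the reported treatment contrast nearly arbitrary too. Odds ratios from neighbouring periods might then not be on the same scale.

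**Working it through.** The plan gives no figure for either model, so there is none to reproduce on this point.

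**1. Number of periods in (e).** Under SAP 3.2.12 the 12-hour period "is defined as the number of hours between the date/time of stool recorded in the DEB and the date/time of first IMP intake". Visit 3 is on Day 9 or Day 10, about (9 - 1) × 24 = 192 h or (10 - 1) × 24 = 216 h after first intake. 192/12 = 16 and 216/12 = 18. Depending on clock times this spans 16 to 19 periods.

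**2. Parameters against rank.** The marginal covariance is V = s²J + R, with J a matrix of ones and R unstructured. V has k(k+1)/2 distinct elements; the model has one parameter more.

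| Periods k | Parameters | Rank |
|---|---|---|
| 8 | 37 | 36 |
| 16 | 137 | 136 |
| 19 | 191 | 190 |

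Cutting the number of intervals, the SAP's first remedy, leaves the excess at one.

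**3. Effect on estimates in (e).** In simulated data (8 periods, n = 200), s² was set to 0, 0.1, 0.2 and 0.548 with R adjusted to match. Each time -2 log-likelihood was 4701.7175, the treatment estimate -0.0893 and its SE 0.1076. With 18 periods and 854 subjects the log-likelihood (-13796.7547) and treatment SE (0.10536) were also the same for every s² tried from 0 to 0.94. A converged fit is therefore unaffected.

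**4. Identification in (a), subject-level reading.** The model is P(Y > k | u) = expit(-θₖ + β·treatment + σu), with u standard normal. Two arms and five categories give 2 × 4 = 8 free cell probabilities. There are 6 parameters: four thresholds, β and σ. If the true odds ratio is 1 there is no departure between arms and σ is not identified at all.

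**5. Likelihood profile.** Inputs: 427 per arm (SAP 1.2.1) and an assumed placebo split of 40/25/20/10/5% over scores 0 to 4. The documents give no pain distribution. The true σ was 0, expected counts were used, and the other parameters were re-maximised at each fixed σ.

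| σ fixed at | 0 | 1 | 2 | 3 |
|---|---|---|---|---|
| Odds ratio | 0.70 | 0.66 | 0.57 | 0.48 |

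From σ = 0 to σ = 3, -2 log-likelihood changes by 0.14 and the treatment likelihood-ratio chi-square goes from 8.03 to 7.89 (difference 0.14). At a true odds ratio of 0.50, the fitted value goes to 0.24, -2 log-likelihood moves by 0.52 and the chi-square goes from 29.1 to 28.6. The test barely changes; the estimate changes a great deal. Placebo splits of 20/25/30/18/7% and 60/20/12/6/2% also take 0.70 to 0.48.

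**6. Simulation.** There were 400 simulated periods at a true odds ratio of 0.70 and true σ = 0, with σ searched from 0 to 5. The best σ was 0 in 46% and 3 or more in 40%. The 5th to 95th percentile range of the odds ratio was 0.20-0.84 with the intercept and 0.57-0.87 without. The 20/25/30/18/7% split gave 0.23-0.82 against 0.58-0.86.

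Under another assumed split (45/25/18/9/3%), with 200 simulations per scenario and σ allowed beyond 5:

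| True odds ratio | With intercept | Without |
|---|---|---|
| 1.0 | 0.32-3.08 | 0.82-1.20 |
| 0.75 | 0.06-0.90 | 0.63-0.93 |
| 0.6 | 0.001-0.71 | 0.47-0.77 |

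**The case against.** The code is redacted, so in (e) the wording may only identify the unit on which measures are repeated. The protocol model and the term list in (f) point that way, and SAP section 5 declares no changes from the protocol. That supports a wording error as the cause, but the text as written still specifies both terms and needs correcting.

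Redundancy does not imply non-convergence. A small trial with a generic optimiser (6 periods, n = 200, complete data) converged in 40 of 40 runs to the same likelihood as without the extra term. Sparse late periods, since only unrecovered subjects continue to Visit 3, are probably the larger threat, and SAP 4.3 requires log review. This stands: no failure rate has been shown. The check was not in SAS and had far fewer periods, so it does not exclude the risk.

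The pain intercept could be for centre; 90 centres are planned. If so, the pain figures above do not apply. This also stands, and it is why the unit must be named.

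The lower limit of 0.20 depends on stopping the search at σ = 5. In a 150-run repeat, the 5th percentile was 0.24 with the cap at 5, 0.14 at 7 and 0.07 at 10. The limit is therefore not a fixed property of the plan, but the cap understates the instability.

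An unadjusted pain comparison is valid in a randomised trial, and model (g) already analyses presence of pain with baseline adjustment. The covariate is an improvement, not the repair of an error, and its gain was not quantified.

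**Conclusion.** The point holds. In (e) the redundancy is exact and rests on no data assumption. It changes no estimate or standard error if the fit converges, and its cost is an avoidable convergence risk of unknown size.

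In (a), a subject-level intercept in separate per-period fits leaves the variance almost unidentified. The odds ratio can then move from 0.70 to 0.48 or beyond with virtually no change in fit. That result rests on the subject-level reading, assumed pain distributions and maximum-likelihood estimation; the SAP's estimation method cannot be seen.

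SAP 3.1.4 makes only the primary analysis confirmatory, so the trial's main conclusion is untouched. The change is still worth making, because these models supply the estimates for a stated secondary objective.

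**What to change.** 1. In (e), and in (f) if it inherits the term, delete the subject random effect. Keep the protocol's unstructured matrix over the planned periods. Name a simpler covariance structure, such as heterogeneous Toeplitz, to be tried before non-convergence leads to the rank tests.
2. In (a), delete the random intercept from the per-period fits; this is the smallest change. The alternative is one cumulative logit model over all periods with treatment, period, treatment-by-period and a subject random intercept, stating that its odds ratios are subject-specific. Choose one before unblinding. If a unit other than the subject was meant, name it.
3. Add baseline abdominal pain (yes/no) to (a), in line with (g), and state that the odds ratio is then conditional on it.

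The cost is SAP wording and model code. No new data are needed; the joint pain model takes slightly more modelling work.
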